12.2 Sample Size/Accrual Rate

N=93 subjects per treatment arm (186 total). With approximately 93 patients in each treatment arm, a two-sample chi-square test with a 0.05 two-sided significance level will have 80% power to detect a difference in the 30-day mortality proportion between treatment arms of 12 % or greater. This calculation assumes a 30-day mortality proportion of approximately 15 % in the intermediate dose prophylaxis arm.

12.3 Stratification Factors

None

12.4 Analysis of Endpoints

12.4.1 Analysis of Primary Endpoints

The chi-square test will be used to compare the proportion of patients who die by 30 days between the two treatment arms. A two-sided 95% confidence interval for the difference in the 30-day mortality proportion between the two arms will be calculated to assess the precision of the obtained estimate. All other efficacy outcome proportions and safety outcome proportions will be compared between the two treatment arms by the chi-square test or Fisher's exact test, as appropriate. Two-sided exact Clopper-Pearson 95% confidence intervals will be calculated for treatment arm differences, as appropriate. Participants who are discharged prior to day 30 for whom vital status cannot be assessed will be censored from the analysis. We expect this to occur only rarely.

12.4.2 Analysis of Secondary Endpoints

Length of ICU stay: We will compare the length of stay between arms using student's t-test. The length of time will be the total length of time in the ICU during the 30 days. This can be continuous or non-continuous time (i.e. a subject is discharged from ICU and then readmitted to ICU).

Thrombosis composite endpoint: All participants will be categorized as having developed one of the components of the composite endpoint or not through 30 days. The endpoint will be analyzed using chi-square test as described for the primary endpoint. We will also graphically display time to event. We will report the proportion of subjects in each diagnosed with each of these components. The primary analysis will censor participants who die without known thrombotic event. A supporting analysis will consider these deaths as part of the endpoint.

Safety Outcomes: All participants will be categorized as having developed a major bleeding events or a non-major clinically significant bleeding event and we will compare the proportions using chi-square test as described for the primary endpoint. We will also report major and non-major clinically significant bleeding event separately by arm.

Note: All secondary endpoint outcome proportions will be compared between the two treatment arms by the chi-square test or Fisher's exact test, as appropriate. Two-sided exact Clopper-Pearson 95% confidence intervals will be calculated for treatment arm differences, as appropriate.

All p-values will be two-sided with statistical significance evaluated at the 0.05 alpha level. Ninety-five percent confidence intervals for all parameters of interest will be calculated to assess the precision of the obtained estimates. All analyses will be performed in R Version 3.6.1 (R Foundation for Statistical Computing, Vienna, Austria). Note: The statistical considerations section was written in conjunction with the Division of Biostatistics, Department of Population Health Sciences.

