12.6.2 Evaluation of Response

All subjects included in the study will be assessed for response to treatment according to the intention to treat (ITT).

13. Adverse Event Reporting Requirements

Adverse event (AE) monitoring and reporting is a routine part of every clinical trial. The investigator will be required to provide appropriate information concerning any findings that suggest significant hazards, contraindications, side effects, or precautions pertinent to the safe use of the drug or device under investigation. Safety will be monitored by evaluation of adverse events reported by subjects or observed by investigators or research staff, as well as by other investigations such as clinical laboratory tests, x-rays, computed tomography (CT), electrocardiographs, etc.

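### ICU stay is compared by t-test on total ICU days with no allowance for death, so a mortality difference alone can move the result in either direction

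*Combined protocol and SAP*

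**What the plan says.** Section 12.4.2 defines the variable: "The length of time will be the total length of time in the ICU during the 30 days". Separate ICU spells are added together. The test is also given: "We will compare the length of stay between arms using student's t-test". Nothing is said about patients who die within the 30 days.

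Section 12.6.2 keeps them in the comparison: "All subjects included in the study will be assessed for response to treatment according to the intention to treat".

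The next paragraph of Section 12.4.2 does deal with death, but only for the thrombosis composite. It gives a main rule, "The primary analysis will censor participants who die without known thrombotic event", and an alternative, "A supporting analysis will consider these deaths as part of the endpoint".

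Section 12.4.1 has one further rule, for the primary endpoint: "Participants who are discharged prior to day 30 for whom vital status cannot be assessed will be censored from the analysis". It concerns unknown vital status after discharge, not known deaths.

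The objective in Section 1.2.2 asks whether therapeutic anticoagulation shortens ICU stay, so fewer days are read as benefit.

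**The concern.** Death ends ICU time. Under the stated definition, a patient who dies in ICU on day 4 contributes 4 days, which looks better than a survivor who leaves ICU on day 14. The trial is sized for a mortality difference, with "80% power to detect a difference in the 30-day mortality proportion between treatment arms of 12 % or greater". If that hypothesis is true, it distorts the ICU comparison. The arms then differ in how many stays were cut short by death, and mean ICU days move even if treatment changes ICU time in nobody else.

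The distortion could make a treatment that saves lives appear to lengthen ICU stay, or appear to shorten it. If therapeutic dosing raised mortality, the arm with more deaths could look better on this endpoint. The plan gives no second analysis that would help a reader tell these cases apart.

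**Working it through.** **The plan's own figure.** Section 12.2 gives 93 per arm for 15% control mortality and a 12-point difference. With the pooled chi-square formula at 15% vs 3%, n = [1.960·√(2 × 0.09 × 0.91) + 0.842·√(0.15 × 0.85 + 0.03 × 0.97)]² / 0.12² = 88.1, so 89 per arm. Power at 93 is 82.1%. A rate of 15.5% vs 3.5% gives exactly 93, which fits a control rate given as approximate. The small gap is on the safe side and does not bear on this point. No power, SD or expected difference is given for ICU stay.

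**Inputs.** From Section 12.2: 93 per arm, 15% control mortality, a 12-point difference. Assumed, because the documents are silent: D, mean ICU days in patients who die; R, the mean in patients whose death is averted; S, the mean in other survivors.

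**Formula.** At 15% vs 3%, with ICU time unchanged in everyone else:

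- Control mean = 0.15·D + 0.85·S
- Therapeutic mean = 0.03·D + 0.12·R + 0.85·S
- Shift (therapeutic minus control) = 0.12 × (R − D)

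For R = S = 14 and D = 8, the control mean is 1.20 + 11.90 = 13.10, the therapeutic mean is 0.24 + 1.68 + 11.90 = 13.82, and the shift is +0.72 days.

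**t-test at 15% vs 3%.** Simulation with 93 per arm, gamma stays (shape 2) capped at 30 days, and 10,000 trials per row:

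| S | R | D | 0.12 × (R − D) | Simulated shift | p<0.05 |
|---|---|---|---|---|---|
| 14 | 14 | 5 | +1.08 | +1.07 | 13.9% |
| 14 | 14 | 8 | +0.72 | +0.72 | 8.9% |
| 14 | 14 | 12 | +0.24 | +0.27 | 5.7% |
| 14 | 14 | 14 | 0 | 0.00 | 5.2% |
| 14 | 20 | 5 | +1.80 | +1.79 | 28.6% |
| 14 | 20 | 8 | +1.44 | +1.45 | 20.3% |
| 14 | 8 | 14 | −0.72 | −0.71 | 8.3% |
| 8 | 8 | 14 | −0.72 | −0.72 | 12.2% |

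The standard error of the difference is 1.2 to 1.3 days with S = 14 and 0.9 with S = 8.

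**Other mortality differences.**

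- 15% vs 7%: 0.08 × (14 − 8) = 0.48 days, p<0.05 in 6.7% (S = 14). With R = 20, D = 5: 1.20 days, 15.4%.
- 15% vs 11%: 0.04 × (14 − 8) = 0.24 days, 5.0%. With R = 20, D = 5: 0.60 days, 7.5%.
- 15% vs 27%: the sign flips. With S = 14, R = 20, D = 5 the shift is −1.80 days, p<0.05 in 28.9%, and the arm with more deaths appears to have the shorter stay.
- Equal mortality: the t-test rejects in 5.0% to 5.1%.

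**A death-aware alternative under the same conditions.** The measure is ICU-free days (30 minus ICU days), with death ranked below 0 and a Wilcoxon rank-sum test. At 15% vs 3%, with only mortality changed, approximate rates of p<0.05 are:

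| S, R, D | t-test | Wilcoxon |
|---|---|---|
| 14, 14, 8 | 9% | 28% |
| 14, 14, 12 | 5% to 6% | 30% |
| 8, 8, 14 | 12% | 29% |
| 14, 8, 5 | 6% | 49% |
| 14, 20, 5 | 29% | 16% |
| 14, 20, 8 | 20% to 21% | 17% |

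It favours the lower-mortality arm in about 82% to 98% of trials at a 12-point difference in either direction. At equal mortality it rejects in 4.3% to 5.3%. Death is ranked below 0 because, with S = 14, 8.7% of survivors reach the 30-day cap and would otherwise tie with the dead.

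**The case against.** **The variable is fully defined.** Every patient, including each one who dies, has a value, and total ICU days is a coherent description of ICU use. This stands, and it is why total ICU days should stay in the plan. It does not answer the point, because the objective reads fewer days as benefit and the definition lets early death supply them.

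**The death-aware measure responds to mortality even more.** This also stands. With only mortality changed, it rejects in about 16% to 50% of trials, in most scenarios more often than the t-test. A reader might infer that replacing the t-test with ICU-free days would give a clean test of ICU stay. It would not. What it gains is a direction that usually agrees with survival.

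**The size rests on assumptions.** True. The largest figures need the full 12-point difference together with averted deaths that stay far longer in ICU than other survivors (R = 20 against S = 14). At 15% vs 11% with R = S = 14 and D = 8, the rejection rate cannot be told from nominal.

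**Some patients may have no ICU time.** Section 4.2 admits non-ICU patients. If 30% to 50% of other survivors have zero ICU days (an assumption), the t-test rate at R = 14, D = 8 is 8.3% to 8.6%, while the Wilcoxon rate falls to 15% to 17%. The power of the alternative is therefore not established for this population.

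**Unknown vital status is a separate matter.** Section 12.4.1 says of it: "We expect this to occur only rarely". Best-case and worst-case analyses for those patients are not part of this point.

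**Conclusion.** The concern holds as a fault in how one secondary endpoint is analysed and read. Following Section 12.4.2 exactly, a t-test difference in ICU days cannot be separated from a difference in mortality. The treatment of the thrombosis composite in the same section shows that handling death is within the plan's own approach.

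At 15% vs 3% the shift is about −0.7 to +1.8 days over the values tabulated, with p<0.05 in about 5% to 29% of trials. These values are assumptions, not bounds: R = 8, D = 20 would give 0.12 × (8 − 20) = −1.44 days. The shift is zero at R = D or at equal mortality, and about 0.5 days (6.7%) at 15% vs 7% with R = S = 14, D = 8.

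Two stronger readings are not supported. A reader might infer that the analysis is biased against the therapeutic arm, but the documents give neither R nor D, so the direction is open. A reader might also infer that the main result is at risk, but the mortality comparison in Section 12.4.1 does not use ICU days.

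**What to change.** Make two changes in Section 12.4.2 before outcome data by arm are seen.

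1. Keep total ICU days. Report it by arm, separately for survivors and decedents, beside 30-day mortality. State that a t-test difference will not on its own be read as a treatment effect on ICU stay.
2. Pre-specify one death-aware comparison, as the plan already does for the thrombosis composite. One option is ICU-free days to Day 30 with death ranked below 0, compared by the Wilcoxon rank-sum test, reporting the probability that a therapeutic-arm patient does better with its 95% CI. Word any conclusion as *alive and out of ICU*, not as an effect on length of stay.

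**Cost.** No new data: ICU time over the 30 days and 30-day death are already needed for planned endpoints. The edit is a few sentences, with a matching line in Sections 1.2.5 and 12.1 if the added measure is to be named there.

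**Downside to state in the plan.** The added measure contains mortality and overlaps the primary endpoint, so its components must be shown with it. Its power is lower if many survivors have no ICU time.

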1.2.2 Secondary Objectives

1. To assess if therapeutic anticoagulation reduced the length of ICU stay.
2. To determine if therapeutic anticoagulation reduces the number of documented venous thromboembolism (VTE), arterial thrombosis (stroke, myocardial infarction other) and micro thrombosis.
3. To evaluate if therapeutic anticoagulation leads to increase major and clinically relevant non-major bleeding events as defined by the International Society of Thrombosis and Haemostasis (ISTH) criteria.

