12.1.1 Primary Endpoint: Death at 30 days (primary)

12.1.2 Secondary Endpoint: Length of ICU stay.

12.1.3 Secondary Endpoint: Composite endpoint of:

- Objectively documented pulmonary embolism
- Objectively documented confirmed proximal deep vein thrombosis (DVT) of the upper or lower extremities.
- Objectively documented micro-thrombosis (skin biopsy).
- Objectively documented thrombosis of the dialysis, continuous renal replacement (CRRT) filters.
- Objectively documented arterial thrombosis (stroke, myocardial infarction, limb ischemia).

12.1.4 Secondary Endpoint: Safety Outcomes of major bleeding and clinically relevant non-major bleeding events defined as:

Major bleeding, defined (as per ISTH guidelines) as acute clinically overt bleeding associated with one or more of the following:

A decrease in hemoglobin of 2 g/dL or more;
A transfusion of 2 or more units of packed red cells;
Bleeding that occurs in at least one of the following critical sites:

- i. Intracranial
- ii. Intra-spinal
- iii. Intraocular (within the corpus of the eye; thus, a conjunctival bleed is not an intraocular bleed)
- iv. Pericardial
- v. Intra-articular
- vi. Intramuscular with compartment syndrome
- vii. Retroperitoneal

Bleeding that is fatal; Bleeding that necessitates surgical intervention.

Clinically relevant non-major bleeding event, defined as acute clinically overt bleeding that does not meet the criteria for major and consists of;

- a) Any bleeding compromising hemodynamics;
- b) Spontaneous hematoma larger than 25cm², or 100cm² if there was a traumatic cause;
- c) Intramuscular hematoma documented by ultrasonography;
- d) Epistaxis or gingival bleeding requiring tamponade or other medical intervention or bleeding from venipuncture for >5 minutes;
- e) Hematuria that was macroscopic and was spontaneous or lasted for more than 24 hours after invasive procedures;
- f) Hemoptysis, hematemesis, or spontaneous rectal bleeding requiring endoscopy or other medical intervention;
- g) Clinically relevant bleeding defined as the composite of major and clinically relevant non-major bleeding;
- h) Permanent early discontinuation of the anticoagulant due to safety reasons.

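### The thrombosis chi-square test “censors” patients who die without known thrombosis; read as removal, this makes the denominator depend on death and contradicts the plan's own all-participants and ITT rules

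*Combined protocol and SAP*

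**What the plan says.** Section 12.4.2 sets out the thrombosis composite in this order:

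- Population and outcome: "All participants will be categorized as having developed one of the components of the composite endpoint or not through 30 days".
- Test: "The endpoint will be analyzed using chi-square test as described for the primary endpoint".
- Time to event is to be displayed graphically. No curve method is named.
- Deaths, main analysis: "The primary analysis will censor participants who die without known thrombotic event".
- Deaths, second analysis: "A supporting analysis will consider these deaths as part of the endpoint".

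Three other places bear on how to read this:

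- Section 12.4.1, on the primary chi-square test: "Participants who are discharged prior to day 30 for whom vital status cannot be assessed will be censored from the analysis". There the word plainly means left out.
- Section 12.6.2 puts all subjects under intention to treat for response, and Section 10.1 lists the thrombosis objective among the response criteria.
- The objective in Section 1.2.2 concerns the number of documented events, and every component of the composite in Section 12.1.3 must be objectively documented.

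**The concern.** A chi-square test on a yes/no outcome has no censoring, so the sentence on deaths can mean three things: these patients are removed, they count as no event, or the rule applies only to the graph. On the third reading the chi-square rule for deaths is unstated. The plan does not say which is meant.

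Removal is the most natural reading, given the wording of 12.4.1 and the instruction to analyse as for the primary endpoint. It would define the excluded group by a post-randomisation event that is itself the primary endpoint. The exclusion in 12.4.1 concerns unknown outcomes and is expected to be rare. This one could take out roughly 6 to 14 of 93 control patients at the planned mortality.

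Because the endpoint is documented thrombosis, a patient who dies without a documented event has a known result on it. Removing such patients raises the observed thrombosis rate more in the arm with more of these deaths, and so favours the other arm without any effect on thrombosis. The supporting analysis does not repair this, because it takes in the whole between-arm difference in deaths without thrombosis.

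**Working it through.** **Inputs.** From Section 12.2: 93 per arm, control mortality 15%, detectable difference 12 points (15% vs 3% if therapy is better), two-sided 0.05. From Section 3.2: thrombosis risks of 31%, 25% and 43% in cited ICU studies. Applying one of these to both arms is an assumption, since the plan gives no expected thrombosis rate. So is the link between thrombosis and death.

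**The plan's own figure.** The plan gives none for thrombosis. For mortality, the pooled chi-square formula without continuity correction gives 89 per arm for 15% vs 3%. With 93 per arm, power is 82.1% and the difference detectable with 80% power is 11.75 points. The stated 93 is slightly conservative and does not affect this point.

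**Rate after removal.** Let p be the documented thrombosis risk, d mortality, and RR the risk of death with versus without thrombosis. The share removed is m = (1−p)·d / (1+p(RR−1)), or m = d if every death occurs without thrombosis. The rate after removal is p/(1−m).

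With p = 0.31 and RR = 1:

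- Control: m = 0.69 × 0.15 = 0.1035, so 9.6 patients are removed; 0.31/0.8965 = 34.6%.
- Therapy at 3%: m = 0.69 × 0.03 = 0.0207, so 1.9 patients are removed; 0.31/0.9793 = 31.7%.
- Difference: 2.9 points, where the true difference is 0.

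Spurious difference in points (positive favours therapy), control mortality 15%:

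| Therapy mortality | RR = 1 | RR = 2 | RR = 3 | All deaths without thrombosis |
|---|---|---|---|---|
| 3% | 2.9 | 2.2 | 1.7 | 4.5 |
| 10% | 1.3 | 0.9 | 0.7 | 2.0 |
| 15% | 0 | 0 | 0 | 0 |
| 20% | −1.4 | −1.0 | −0.8 | −2.3 |

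At 15% vs 3%, the range over the same four cases is 1.65 to 3.64 points for p = 25% and 1.67 to 6.26 for p = 43%. For scale, the standard error of the difference is √(2 × 0.31 × 0.69/93) = 6.8 points.

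**False-positive rate** (simulated, 93 per arm, p = 31%, nominal 5%; the plan does not say whether the test is continuity-corrected):

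| Mortality, dependence | Removal, uncorrected | Everyone kept, uncorrected | Removal, corrected | Everyone kept, corrected |
|---|---|---|---|---|
| 15% vs 3%, RR = 1 | 7.0% | 5.1% | 5.0% | 3.4% |
| 15% vs 3%, all four cases | 5.8–9.7% | 5.1–5.2% | 4.0–7.1% | 3.4–3.5% |
| 15% vs 10%, RR = 1 | 5.5% | 5.2% | 3.8% | 3.5% |

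**What removal assumes.** Since p/(1−m) = p + m·[p/(1−m)], removal is the same as giving the removed patients the event rate of those kept: 34.6% of 9.6 = 3.3 events in control and 31.7% of 1.9 = 0.6 in therapy (RR = 1). It is not neutral about thrombosis missed before death.

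**Supporting analysis.** Its rate is p + m. With no thrombosis effect it shows 41.35% vs 33.07%, or 8.3 points, at 15% vs 3% (5.1 to 12.0 over the four cases). At 15% vs 10% it shows 3.45 points (2.1 to 5.0). All of this comes from deaths.

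**If the target were the thrombosis hazard.** Take constant hazards, the same net thrombosis risk of 31% in both arms, and deaths of 15% vs 3%. Cumulative incidence is then 28.76% vs 30.56%, 1.8 points against therapy. Removal gives 32.90% vs 31.35%, about 1.6 points in favour of therapy. At 15% vs 10% cumulative incidence is 28.76% vs 29.52%, 0.8 points against therapy.

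**The case against.** **The reading.** Section 12.4.1 speaks of being censored from the analysis, for patients whose status is unknown. Section 12.4.2 says only that these deaths are censored and contrasts this with counting them as events, which could mean that they count as no event. On that reading there is no contradiction and no bias. This is a fair possibility, but the plan does not state it. If it is what was meant, the fix puts the intention into words.

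**Undetected thrombosis.** The plan's word *known*, and the autopsy micro thrombi in Section 2.1, point to events missed before death. Suppose a share f of deaths without a documented event hid one (RR = 1, 15% vs 3%). The true difference is then f × 0.69 × 0.12, which is 2.07 points at f = 25% and 4.14 at f = 50%. Keeping everyone misses all of that. Removal shows 2.92 whatever f is, so it errs by 0.85 and 1.22 points. Removal is closer once f exceeds 2.92/(2 × 8.28), about 18%. This stands as a limit of the documented endpoint. It does not justify removal as the main rule, because the protocol defines the endpoint by documentation and removal imputes a rate without saying so.

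**Size.** A fall in mortality from 15% to 3% with no effect on thrombosis is an extreme case. The cited thrombosis risks come from ICU patients, whereas Section 4.2 also admits non-ICU patients. At an assumed 15% risk and RR = 1 the shift is 1.8 points (15% vs 3%) or 0.8 (15% vs 10%). With continuity correction the false-positive rate stays at or below 5.0% for RR of 1 to 3. All of this stands: the effect is modest, and the case for change does not rest on it.

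**Scope.** One sentence would cure the ambiguity. The hazard ratio and the autopsy rule are useful but optional.

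**Conclusion.** The concern holds. The rule on deaths cannot be carried out in a chi-square test as written, and its most natural reading contradicts both its own paragraph and ITT. For the endpoint the protocol defines, documented thrombosis by Day 30 in all participants, removal is biased whenever the arms differ in deaths without thrombosis. With 31% thrombosis in both arms, the bias is 1.7 to 4.5 points at 15% vs 3% mortality and 0.7 to 2.0 at 15% vs 10%. It is zero at equal mortality and goes against therapy if therapy mortality is higher. These figures rest on the assumed thrombosis risk, on its equality across arms, and on the stated dependence cases; 15% vs 3% is the detectable difference, not an expected one. The primary endpoint is untouched and the shift is well below one standard error, so this is something that should be fixed rather than a threat to the trial. In an open-label study the rule should be settled before outcomes by arm are seen.

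**What to change.** Replace the sentence on censoring in Section 12.4.2 with wording such as:

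> All randomised participants stay in the denominator; none is removed because of death. A participant who dies by Day 30 without a documented thrombotic event is counted as having no documented event. Time to thrombosis is displayed as cumulative incidence (Aalen-Johansen) with death as a competing event.

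Make the Day-30 risk difference with its 95% confidence interval the main result. In the same table show thrombosis-or-death (the opposite extreme for deaths whose thrombosis status is unknown), 30-day mortality, and the number of deaths without documented thrombosis in each arm. State in advance whether thrombosis first found at autopsy counts as documented. A cause-specific hazard ratio is a useful optional addition.

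The cost is SAP wording and a little programming. No new data are needed unless autopsy findings are to count, since the schedule of assessments (Table 1) lists no autopsy item. The SAP should name two downsides. With an unchanged thrombosis hazard, cumulative incidence rises in the arm with fewer deaths, by about 1.8 points at 15% vs 3% and 0.8 at 15% vs 10%. Thrombosis missed before death is under-counted, more so in the arm with more deaths. Documented thrombosis, thrombosis-or-death and mortality therefore have to be read together.
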